8.11 Multiple Comparisons and Composite Endpoints

With the primary hypothesis and the various secondary endpoints, there is a multiplicity of analyses to be performed and an increased probability that at least one of the comparisons could be "significant" by chance. There are adjustments (e.g., based on the Bonferroni inequality) that can be used to preserve the overall type I error level by adjusting for the multiplicity of secondary endpoints by requiring small significance levels for every comparison. We will be conservative in the interpretation of these analyses, taking into account the degree of significance, and looking for consistency across endpoints. Also, we have pre-specified the primary and secondary outcome variables to help avoid over-interpretation and to reduce the problems inherent with multiple testing. A related issue is the interpretation of composite endpoints in clinical trials. To understand the importance of the components of the primary endpoint, we will estimate the treatment effect and frequency of each component (CV mortality and HF hospitalization) separately. Based on the prior biomarker-guided studies in HF, we have pre-specified age (\geq 75 or < 75 years of age) as a key subgroup of interest. The examination of this subgroup will include a formal test of interaction with the Cox regression model. Hazard ratio plots with point estimates and 95% confidence intervals will be used to examine the consistency of the treatment effect across subgroups.

8.12 Exploratory Endpoints

In order to explore the contribution of recurrent hospitalization and quality of life to the overall efficacy and safety of biomarker guided therapy, alternative methodologies for assessing multiple endpoints will be analyzed. These will include the global rank approach as previous described⁵¹. Generally, a pre-specified hierarchy of endpoints will be created that will include death, hospitalization, and quality of life. All patients will be ranked according to this hierarchy, and the primary statistical comparison will be the

comparison of ranks between the treatment and control group. An alternative approach to be explored will be the "win ratio" as described by Pocock et al⁵². In this approach, patients randomized to biomarker guided therapy and control will be matched based on baseline characteristics, and the overall post randomization experience between each pair will be compared using a pre-specified hierarchy of endpoints in order to determine a "winner". The primary metric will be the proportion of pairs with the biomarker guided arm wins relative to control.

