6.2 Randomization

Subjects who fulfill all the inclusion criteria and none of the exclusion criteria will be randomized in a 1:1 fashion using the Simple Internal Randomization Engine (SIRE) system to either biomarker-guided therapy or usual care. The unit of randomization will be at the patient level rather than the site level. Treatment allocation will be conducted using a complete randomization scheme. At randomization, subjects will undergo a brief interval history and physical exam, cardiovascular (CV) medication history, local laboratory testing for renal function and electrolytes, assessment for adverse events, 6 minute walk test, QOL questionnaires, medical resource use and cost assessment, and core laboratory samples.

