7.3 Exploratory Endpoints

• Global Rank Endpoint, incorporating death, hospitalization, and change in quality of Life

• Win-ratio, incorporating death, hospitalization, and change in quality of life

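### The exploratory win ratio is fixed as one win or loss per matched pair; comparing all pairs within baseline-risk strata would be more precise and would leave no patient unpaired

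*Protocol*

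**What the plan says.** Protocol section 7.3 lists two exploratory endpoints on the same outcomes: a global rank and "Win-ratio, incorporating death, hospitalization, and change in quality of life".

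Section 8.12 describes both.

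- **Global rank.** Under this approach "a pre-specified hierarchy of endpoints will be created that will include death, hospitalization, and quality of life". Then "All patients will be ranked according to this hierarchy, and the primary statistical comparison will be the" comparison of ranks between the arms.
- **Win ratio, as the alternative.** Here "patients randomized to biomarker guided therapy and control will be matched based on baseline characteristics, and the overall post randomization experience between each pair" is compared, and each pair yields a winner. "The primary metric will be the proportion of pairs with the biomarker guided arm wins relative to control".

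The matching variables are not named, and no power, precision or effect size is claimed for the win ratio. On allocation, section 6.2 states: "Treatment allocation will be conducted using a complete randomization scheme". Section 5 gives about 550 patients per arm.

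**The concern.** The pairing rule and the metric are stated in the protocol, so an SAP that used all pairs would depart from it. With about 550 per arm there are at most about 550 binary results, in effect a sign test, out of 550 × 550 = 302,500 possible guided-versus-control comparisons.

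Three things are at stake, all modest:

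- The interval for the win ratio may be wider than the data require.
- Some randomized patients drop out of the analysis because the arms will rarely be equal in size.
- The win ratio and the global rank may differ partly because one uses far fewer comparisons. Section 8.11 intends to look for consistency across endpoints, so such a difference could be misread.

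**Working it through.** **Plan's own figure.** There is none for the win ratio. As a check on the design inputs only, a simulation from section 8 (40% v 32% at 1 year, 35 patients per month, 12 to 24 months of follow-up, 4% + 4% yearly censoring, 5% crossover) gave 88.9% power and 566 events, against 89.4% and 566 stated.

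**Step 1: no gain from matching, no ties, n = 550 per arm.** Variance of the win proportion under the null:

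- matched pairs: 1/(4n) = 1/2,200 = 0.000455
- all pairs: (2n + 1)/(12n²) = 1,101/3,630,000 = 0.000303, about 1/(6n)

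The ratio is 2/3, so one third of the information is lost and the interval is √1.5 = 1.22 times as wide.

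**Step 2: allow for matching, against unstratified all pairs.** Under a normal model, a within-pair correlation ρ gives relative information (2/3)/(1 − ρ). If all-pairs power is P, matched power is Φ{[1.96 + Φ⁻¹(P)] × √[(2/3)/(1 − ρ)] − 1.96}.

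| ρ | Information lost | Matched power when P = 60% | P = 80% | P = 90% |
|---|---|---|---|---|
| 0 | 33% | 43.9% | 62.8% | 75.4% |
| 0.1 | 26% | 47.8% | 67.4% | 79.7% |
| 0.2 | 17% | 52.4% | 72.5% | 84.1% |
| 0.3 | 5% | 57.9% | 78.1% | 88.6% |
| 1/3 | 0% | 60% | 80% | 90% |

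Above 1/3 the matched analysis is the better of the two. The protocol gives nothing that fixes ρ.

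**Step 3: against all pairs within risk strata.** Hierarchy simulations used death, then HF hospitalization, then QOL, with 550 per arm over 12 months. Control mortality was 25% with a 25% relative reduction (section 8.4), i.e. 18.75%. Hospitalization rate, QOL effect and prognostic strength were assumed. Matching was on the true risk score, which favours matching. Strata were quintiles of that score.

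*Assumption set A* (composite 1-year rate about 36–44% v 29–36%; 3,000 data sets per setting). Power, matched v stratified:

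| Prognostic strength | QOL effect 0 | 0.10 SD | 0.25 SD |
|---|---|---|---|
| none | 65 v 79% | 79 v 91% | 94 v 99% |
| C-index 0.61 | 60 v 75% | 77 v 90% | 93 v 99% |
| C-index 0.68 | 52 v 67% | 73 v 87% | 93 v 99% |
| C-index 0.75 | 45 v 54% | 70 v 85% | 93 v 99% |

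The gaps are 5 to 15 points on these rounded figures. At C-index 0.68, null rejection was 7.0% for the matched test and 4.6% for the stratified test, so matched power is if anything flattered.

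*Assumption set B* (30% control hospitalization, hazard ratio 0.78; 1,500 runs, Monte Carlo error about 1 point). Power (%), matched / unstratified / stratified:

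| Log-HR per SD, QOL correlation | QOL effect 0 | 0.1 SD | 0.2 SD |
|---|---|---|---|
| none | 66/81/81 | 79/92/92 | 90/97/97 |
| 0.5, 0.3 | 63/74/78 | 80/88/91 | 90/96/98 |
| 0.8, 0.5 | 60/61/73 | 79/81/92 | 91/94/98 |
| 1.0, 0.6 | 59/54/73 | 80/79/93 | 92/92/99 |

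The stratified gain is 7 to 15 points on these rounded figures. The unstratified gain disappears at the strongest setting, as step 2 predicts.

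*Assumption set C* (same mortality, other assumed values) gave a stratified gain of about 7 to 19 points.

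**Step 4: unpaired patients.** Under complete randomization of 1,100, the expected absolute difference in arm size is √1,100 × 0.798 = 33.17 × 0.798, about 26, or 26/1,100 = 2.4% of patients.

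**The case against.** The strongest reply is that no statement in the protocol is wrong. The win ratio is an exploratory alternative with no power claim, it follows a cited published method, and no decision rests on it. That stands, and it limits the point to an efficiency improvement.

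A reader might infer that the plan throws away a third of the information outright. The documents do not support that. Section 8.12 matches on baseline characteristics, and step 2 shows that prognostic matching recovers part or all of the loss. The supportable range is zero to one third. In one check with log-hazard SD 0.7 and QOL correlation 0.3, the within-pair correlation was about 0.175, a loss of about 19%; with 1.0 and 0.5 it was about 0.32, almost no loss.

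A reader might also infer that the trial forgoes the all-patient comparison. It does not. A two-arm comparison of ranks is in essence an all-pairs comparison, so the global rank analysis already uses every patient, including those left unpaired. As described, though, it is unadjusted, so it does not supply the like-with-like comparison that matching was meant to add.

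It is also fair to say that the 5 to 19 points combine two changes, using all pairs and stratifying by risk, and that they rest on assumed inputs. But stratified all-pairs stayed ahead in every setting, including those where unstratified all-pairs did not. Matching variables and tie rules can properly be left to the SAP; the one-to-one rule and its metric are already set.

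**Conclusion.** The point holds as a modest efficiency gain for an exploratory analysis, not as an error. How much matching costs against unstratified all pairs cannot be settled from the protocol, because it turns on the unstated matching variables. The case for change rests on the stratified comparison, where the direction was the same under all three sets of assumptions. The size of that gain depends on the assumed hospitalization rate, QOL effect and prognostic strength. The loss of unpaired patients is small, but it follows directly from combining one-to-one pairing with complete randomization.

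**What to change.** In section 8.12, define the win ratio over all guided-versus-usual-care pairs within strata of baseline risk, for example quintiles of a score built from the section 8.8 covariates (age, sex, NT-proBNP, ejection fraction, diabetes). Judge each pair over its shared follow-up, combine across strata, and report the win ratio with a 95% confidence interval. Keep the matched-pair version as a sensitivity analysis.

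The cost is a sentence or two in the protocol and a few lines of code, with no new data, visits or patients. The small downside is that patients are compared within a risk stratum and not with an individually matched partner.

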8.13 Analysis of Economic and Quality of Life Data

For each of the QQL measures examined in this study, data analysis will proceed in several stages. Initially, we will provide simple descriptive and comparative analyses by intention-to-treat. A nonparametric bootstrap will be used to estimate treatment differences with 95% confidence intervals (CI) and p-values. Since there is currently no consensus in the statistical literature about the best way to deal with the multiple comparisons problem arising from testing each individual scale at each time point separately, we propose two complementary approaches. First, we will pre-specify the overall summary score from the KCCQ and functional status using the Duke Activity Status Index as the primary QOL comparisons of interest and assign all other comparisons to a secondary (descriptive) status. Second, we will fit mixed models, which make use of all available QOL data at each study assessment point. Statistical power estimates for the KCCQ, based on data collected in the HF-ACTION trial demonstrate that we should have > 90% power to detect a ¼ standard deviation difference (about 5 points on a 0-100 scale) in the KCCQ overall score and in the DASI (about 4 points on a 0-58 scale). We expect refusal rates to be quite low overall. In a 2966-patient QOL substudy in GUSTO, we had a 1% refusal rate at each of three interviews. The rate of patient incapacity expected for GUIDE-IT is uncertain, but should be similarly low.

Several important methodologic challenges must be considered in the analysis of QOL data: the effect of differential mortality in the treatment arms and the effect of missing data (from death, incapacity or loss to follow-up). Our approach to missing data is to minimize it as much as possible. If the primary study hypotheses are confirmed, analysis of QOL data may be complicated by the fact that the biomarker-guided strategy was more successful at keeping patients alive. Even a relatively small difference in mortality due to treatment may create a paradox in the QOL data such that the more effective therapy is associated with worse QOL (for example, if the patients with the worst QOL died in the usual care arm but were saved in the biomarker-guided arm.) We will address this problem by estimating the Survivor Average Causal Effects, which involves a counterfactual analysis to predict the QOL scores of interest assuming that the patient had not died or been otherwise unable to provide their own data.

For the economic analyses, the primary statistical comparisons between the two treatment arms will be performed by intention-to-treat. A nonparametric bootstrap will be used to estimate treatment differences with 95% CI and p-values. Estimates and confidence limits around the observed cost differences can be created using several different approaches. In recent work, we have used bootstrap methods for this.

Although our data analysis will not make parametric assumptions about the distributions of costs, we can approximate the precision of our estimates by assuming that costs follow a log-normal distribution. Previous studies suggest that this is a reasonable assumption. For data that are log normally distributed, the coefficient of variation (i.e., the standard deviation divided by the mean) remains constant, an observation that we have seen empirically across different studies and treatment arms. In fact, our experience has shown that the coefficient of variation is very close to 1 (i.e., the standard deviation is equal to the mean). Under the assumption of log normal distributions and CV=1, with > 500 patients (> 90%) with cost data per treatment arm, we will be able to estimate the difference in mean costs between

treatments to within approximately 0.12 standard deviations based on the half-width (1.96 times the standard error) of the 95% confidence interval. This means, for example, if the mean cost per treatment arm was \$10,000, then the 95% confidence interval for the treatment difference in cost would be the point estimate for the difference +/- \$1,208.

In order to provide a second (descriptive) perspective on cost differences for each strategy in GUIDE-IT, we will also directly measure major health care resource items used including hospital days (e.g., intensive care, step-down units, wards) and cardiac procedures (e.g., ICD, VAD placement, catheterization, coronary revascularization, atrial fibrillation ablation) as well as selected smaller ticket items such as outpatient physician and emergency department visits. A basic set of resource data will be collected on the eCRF, and will be supplemented by the additional resource data that can be collected from the detailed hospital billing forms.

To estimate the incremental cost effectiveness of the biomarker-guided approach relative to usual care, we will calculate a base case cost-effectiveness ratio that defines the incremental cost required to add an extra life year with the biomarker-guided strategy relative to usual care. A second series of analyses will calculate the corresponding cost-utility ratio, using utility data from the EQ-5D collected in the GUIDE-IT trial. These analyses will use the societal perspective and a lifetime time horizon so that the estimated incremental cost-effectiveness and cost-utility ratios can be compared with societal benchmarks. Where extrapolations from empirical data and other assumptions are required, they will be based, to the extent possible, on the empirical data from the GUIDE-IT trial and will be accompanied by appropriate examination of the effects of uncertainty using both stochastic methods and sensitivity analyses. For descriptive purposes, we will also calculate within-trial cost-effectiveness and cost-utility ratios, since they do not require any extrapolations. However, these within-trial ratios are limited due to their failure to account fully for long-term benefits and costs, and the absence of comparative benchmarks. At the time of analysis, costs will be adjusted to the most recent year for which the Producer Price Index has been published. Both costs and life expectancy will be discounted to present value at a 3% annual discount rate (with rates from 0 to 7% examined in sensitivity analyses).

Since many of the patients will remain alive at the conclusion of the trial, a method is required for converting observed trial experience into the corresponding lifetime survival and cost figures needed for use in the incremental cost-effectiveness calculations. There are three general methods that we have previously used to make the necessary lifetime extrapolations called for in cost-effectiveness analysis: use of the trial data for extrapolation, use of secondary data sources to base the extrapolations upon, and use of Markov models. GUIDE-IT will provide a rich empirical data set involving up to 2 years of clinical outcome, cost, and utility data, with over 2,000 patient-years of follow-up information. We will use these data in age-based survival models to create estimates for each GUIDE-IT patient of life expectancy, quality-adjusted life expectancy and lifetime medical costs.

The method, in brief, involves 5 basic steps. 1) Using Cox Proportional Hazards regression methodology for left-truncated and right-censored data, we model the hazard of death as a function of age, adjusting for additional prognostic factors through covariates. This model "adjusts for" age as the metric over which the hazard is computed, treats additional prognostic factors as covariates, and stratifies on treatment group (if necessary to satisfy the proportional hazards assumption). By estimating the hazard over the age metric (rather than over the time metric, as is traditionally done), we can produce data-based survival predictions through a much longer time period due to the broad representation of ages in our database. 2) This hazard relationship, which under proportional hazards is well estimated through the age range represented in our data, is used for prediction on a patient-by-patient basis. The predicted survival estimates for each patient

are then combined with the empirical GUIDE-IT survival data and averaged over all the patients for both treatment groups. 3) Again using a Cox Proportional Hazards regression model, together with the post-HF hospitalization survival experience available in the GUIDE-IT data (and if necessary, secondary data sources available at the DCRI including HF-ACTION), we will estimate the long-term survival impact of a HF hospitalization, the non-fatal component of the study primary endpoint. This model will provide a quantitative measure of the increased relative risk attributable to these non-fatal events for later incorporation in the individual patient predictions. 4) For the oldest age range, where the amount of empirical data may not be sufficient, we will use a Gompertz-based function for extrapolation. The estimated mean survival curves are integrated over a lifetime to obtain life expectancy for each treatment group. 5) The difference between the areas under each survival curve is computed to obtain the biomarker-guided arm incremental life expectancy.

Uncertainty in cost-effectiveness estimates related to sampling variation will be quantified using nonparametric bootstrap techniques (1,000 samples with replacement with a cost-effectiveness ratio calculated for each sample) and expressed in three complementary formats. First, cost-effectiveness ratios arising from the bootstrap will be displayed on the cost-effectiveness plane to characterize the precision and magnitude of the estimates. Second, we will examine the net monetary benefit of the intervention, defined as the difference between the increase in effectiveness (valued using the willingness- to-pay threshold per unit of effectiveness), and the increase in cost. Net monetary benefit and associated confidence intervals will be displayed for a range of willingness-to-pay thresholds. Finally, we will plot the cost-effectiveness acceptability curve, which indicates the probability that that the intervention is cost effective (i.e., incremental net benefit > 0) for a range of willingness-to-pay thresholds. We will also perform sensitivity analyses to address uncertainty related to methodological assumptions regarding key parameters. If appropriate, bootstrap analyses will be repeated for alternative parameter values. It must be emphasized that although the general plan of our cost-effectiveness analyses can be specified prospectively, there is clearly an iterative quality to building successful cost-effectiveness models.

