6.7 Quality of Life Assessments

GUIDE-IT will use a battery of validated instruments that build on a disease-specific core, supplemented by generic measures to provide a comprehensive assessment of health related QOL. These assessments of quality of life (QOL) will be performed at baseline by site coordinators and then 3 months, 6 months and annually to a maximum of 24 months by structured telephone interview conducted by the EQOL CC staff. A detailed description of each of these instruments with instructions will be included in the Manual of Operations. Assessments at each visit will include the following:

- Kansas City Cardiomyopathy Questionnaire (KCCQ)
- Duke Activity Status Index (DASI)
- enter for Epidemiological Studies Depression Scale (CES-D)
- Medical Outcomes Study Short Form (SF-12)
- Medical Outcomes Study Short Form (SF-36) subscales: General Health, psychological well-being, vitality, social functioning)
- EQ-5D

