8.6 Sample Size Justification for Secondary Endpoints

In Figure 5, a set of power curves is presented to describe the power to detect treatment effects for secondary endpoints. These power calculations are based on the following assumptions: 2-sided Type I error rate of 0.05, a test statistic based on a 2-sample t-test, and sample sizes ranging from 350 to 550 subjects per treatment group. Mixed models will be used in the analysis of the longitudinal QOL data. However, calculations based on the 2-sample t-test provide a conservative approximation for the power to detect treatment differences. Assuming at least 350 subjects per treatment group, GUIDE-IT will have >90% power for detecting a treatment difference of ¼ standard deviation. For many of the QOL instruments being proposed for this study, a treatment effect size equal to ¼ of a standard deviation is a reasonable benchmark for a clinically meaningful change.

Figure 5. Power curves for secondary endpoints

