8.8 Analysis for the Primary Hypothesis

The statistical comparison of the two randomized arms with respect to the primary endpoint will be a time-to-event analysis, and therefore will be based on the time from randomization to the first occurrence of CV death or HF hospitalization. The Cox proportional hazards regression model will be the primary tool to analyze and assess outcome differences between the two treatment arms. A hazard ratio and 95% confidence interval for summarizing the difference in outcomes between the two treatment arms will be computed using the Cox model. This comparison will constitute the primary statistical assessment of the effect of biomarker guidance versus usual care on overall clinical outcomes. The Cox model will include an indicator variable for treatment group and baseline adjustment variables for age, sex, NT-proBNP, diabetes mellitus and ejection fraction.

In order to select the best set of adjustment covariates, we reviewed prognostic models from other large datasets in chronic HF. We selected covariates based upon the importance of choosing variables with

minimal missing data and adjusted the primary analysis for the following baseline variables: age, sex, NT-proBNP, ejection fraction, and diabetes mellitus.

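### The KCCQ and DASI comparisons in Section 8.13 carry no baseline term although both scores are measured at baseline; the test is valid but gives up precision

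*Protocol*

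**What the plan says.** Protocol Section 6.7 states that the quality-of-life battery, which includes KCCQ and DASI, "will be performed at baseline by site coordinators and then 3 months, 6 months and annually to a maximum of 24 months". Section 6.3.1 and Appendix A also place it at baseline.

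Section 8.13 makes the KCCQ overall summary score and the DASI the primary quality-of-life comparisons and gives all other scales descriptive status. The analysis is staged. It opens with simple descriptive and comparative intention-to-treat analyses, for which "A nonparametric bootstrap will be used to estimate treatment differences with 95% confidence intervals (CI) and p-values". Mixed models using all available assessments follow as a complementary approach. Neither stage mentions a baseline covariate, a change score or a constraint on baseline means, and the section does not say which stage decides.

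Section 8.6 bases the power of these endpoints on "a test statistic based on a 2-sample t-test, and sample sizes ranging from 350 to 550 subjects per treatment group". It concludes: "Assuming at least 350 subjects per treatment group, GUIDE-IT will have >90% power for detecting a treatment difference of ¼ standard deviation". It adds that mixed models will be used for the longitudinal data and that the t-test calculation is conservative. Section 8.13 repeats the claim as "> 90% power to detect a ¼ standard deviation difference (about 5 points on a 0-100 scale) in the KCCQ overall score", with about 4 points for the DASI.

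For the clinical primary endpoint, Section 8.8 does name its covariates: "The Cox model will include an indicator variable for treatment group and baseline adjustment variables for age, sex, NT-proBNP, diabetes mellitus and ejection fraction".

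**The concern.** For a repeatedly measured score, the patient's own earlier value is usually among the strongest predictors of the later one. A raw difference between arms at follow-up leaves that predictor unused: the interval is wider than the collected data require, and any chance baseline difference stays in the estimate. Section 6.2 describes complete randomization and mentions no stratification, so nothing in the allocation limits such imbalance in KCCQ or DASI.

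The mixed models do not settle the matter as described. If baseline enters as one more outcome time with its own free arm effect, the follow-up contrasts gain essentially nothing from it. If it enters as a covariate, or with baseline means held equal across arms, they do.

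At stake is the precision of the two leading quality-of-life results, mainly at the late visits where fewest patients remain.

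**Working it through.** **Inputs from the protocol**
- Two-sided alpha 0.05, two-sample t-test, 350 to 550 per arm (Section 8.6).
- Difference of 0.25 SD (Sections 8.6 and 8.13). About 5 KCCQ points implies SD ≈ 5/0.25 = 20; about 4 DASI points implies SD ≈ 4/0.25 = 16.
- 1:1 allocation, about 550 per arm (Section 5).
- 36 months of enrollment, then 12 months of follow-up after the last patient (Section 3.3).
- Control all-cause mortality of 25% at 1 year, with a 25% relative reduction as one scenario (Section 8.4).
- Loss to follow-up of 4% per year (Table 2 footnote).

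**Assumed.** The protocol gives no baseline-to-follow-up correlation ρ. I take 0.5, with a range of 0.3 to 0.7. Accrual is taken as uniform and the yearly mortality and loss rates as constant.

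**Step 1: the plan's own figure.** The t-test for d = 0.25 gives 91.0% power at 350 per arm and 98.5% at 550. About 337 per arm are enough for 90%. The claim of more than 90% holds without adjustment.

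**Step 2: effect of adjustment.** With baseline as a covariate, the residual variance is multiplied by 1 − ρ² and the interval width by √(1 − ρ²).
- ρ = 0.3: variance × 0.91 (−9%), width × 0.954 (about 5% narrower).
- ρ = 0.5: variance × 0.75 (−25%), width × 0.866 (about 13% narrower).
- ρ = 0.7: variance × 0.51 (−49%), width × 0.714 (about 29% narrower).

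For KCCQ at 350 per arm, the unadjusted half-width is 1.96 × 20 × √(2/350) = 2.96 points. At ρ = 0.5 it is 2.96 × 0.866 = 2.57 points.

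**Step 3: numbers remaining at each visit.**
- 12 months: control 550 × 0.75 × 0.96 = 396. Guided yearly mortality is 0.25 × 0.75 = 0.1875, so 550 × 0.8125 × 0.96 = 429.
- 24 months: only patients enrolled in the first 24 of 36 months can reach this visit, 550 × 24/36 ≈ 367 per arm. Control: 367 × 0.75² × 0.96² ≈ 190. Guided: 367 × 0.8125² × 0.96² ≈ 223.
- If mortality does not differ between arms, the 24-month count is 190 in both.

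**Step 4: power for 0.25 SD**, with effective effect size d/√(1 − ρ²):

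| Patients per arm | Unadjusted | ρ = 0.3 | ρ = 0.5 | ρ = 0.7 | Gain at 0.5 (points) |
|---|---|---|---|---|---|
| 550 / 550 | 98.5% | 99.1% | 99.8% | 100.0% | 1.3 |
| 500 / 500 | 97.7% | 98.5% | 99.5% | 100.0% | 1.8 |
| 396 / 429 (12 months) | 94.8% | 96.4% | 98.5% | 99.9% | 3.7 |
| 350 / 350 (plan's floor) | 91.0% | 93.3% | 96.8% | 99.6% | 5.8 |
| 190 / 223 (24 months) | 71.4% | 75.4% | 83.1% | 94.3% | 11.7 |
| 190 / 190 (24 months) | 68.1% | 72.2% | 80.1% | 92.6% | 12.0 |

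**Step 5: a change score is not a substitute.** Its variance relative to the raw follow-up score is 2(1 − ρ): 1.4 at ρ = 0.3, 1.0 at 0.5 and 0.6 at 0.7. The covariate-adjusted factors are 0.91, 0.75 and 0.51, lower at each of these values.

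**The case against.** The strongest reply is that the protocol is silent on baseline adjustment but does not rule it out. A bootstrap is a way to obtain an interval and a p-value, and it works as well on an adjusted estimate as on a raw one. The simple comparison is only the opening stage. The mixed models that follow could carry baseline, and Section 8.6 treats the t-test as a planning approximation to them. Covariates of a secondary model are commonly left to the statistical analysis plan, which is not shown.

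Much of this stands. A reader might infer that the plan has decided against adjustment, that the two comparisons are biased, or that the power statement is wrong. The documents support none of these. No sentence excludes a baseline term, the unadjusted randomized comparison is valid and its interval already allows for chance imbalance, and the figure above 90% reproduces. A reader might also infer a general loss of 6 to 12 points of power. That range needs ρ = 0.5 and sample sizes of 350 down to 190 per arm; at 350 per arm the gain cannot exceed 9 points whatever ρ is. The 12-point end belongs to month 24, which the protocol never names as the deciding visit and for which it makes no separate power claim.

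What does not stand is that nothing has been specified. Section 8.13 names an estimate, an interval and a p-value for the two leading scales in a comparison it calls simple, without a baseline term, while Section 8.8 lists covariates for the primary model. Followed as written, the first stage gives a wider interval than necessary, and the mixed model remedies this only under a parameterisation the text does not state.

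**Conclusion.** The point holds as one of efficiency. Both primary quality-of-life scores have a baseline value that the described comparison does not use. At an assumed correlation of 0.5, using it would narrow the interval by about 13% at any visit to which that correlation applies.

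In power for ¼ SD, this is worth 5.8 points at the plan's floor of 350 per arm (2.3 to 8.6 over ρ = 0.3 to 0.7), about 4 points at 12 months, and under 2 points at 500 or more per arm (2.3 at most at 500, for ρ = 0.7). It is worth about 12 points at 24 months, where unadjusted power is about 68–71%. The 24-month figure rests on uniform accrual and on the protocol's mortality and loss rates holding for two years; all the gains rest on ρ, which the protocol does not give.

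The endpoint is secondary and no stated figure is wrong, so this is an inexpensive improvement to make before analysis.

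**What to change.** In Section 8.13, or in the statistical analysis plan with a cross-reference:
- Estimate the KCCQ overall summary and DASI treatment differences at each visit with the patient's own baseline score as a covariate (ANCOVA). Keep the bootstrap for the interval and p-value by resampling patients and refitting the model.
- In the mixed model, enter baseline as a covariate, or include it as an outcome with means constrained equal across arms.
- Say which of the two analyses decides for KCCQ and DASI.
- Keep the unadjusted bootstrap difference as a descriptive supplement.

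The cost is a few sentences and one covariate per model, with no new data. Patients with a missing baseline score need simple baseline imputation or the constrained mixed model, so that they are not dropped. The power statement in Section 8.6 can stay, since it is conservative for the adjusted analysis.
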